### 10.3.3 CCI

### 10.3.4 CCI

SAP 331-201-00080

CCI

10.3.5

CCI

10.3.6

CCI

10.3.7

CCI

SAP 331-201-00080

### 10.3.8 C-SSRS

Suicidality will be monitored during the trial using the C-SSRS. This trial will use the “baseline/screening” and “Since Last Visit” versions of the scale. The “baseline/screening” version, which assesses the lifetime experience of the subject with suicide events and suicidal ideation and the occurrence of suicide events and/or ideation within a specified time period prior to entry into the trial, will be completed for all subjects at screening to determine eligibility. Any subject with active suicidal ideation within the last 6 months, suicidal behaviors within the last 2 years, or who in the clinical judgment of the investigator presents a serious risk of suicide should be excluded from the trial. The “Since Last Visit” C-SSRS form will also be completed at all visits after screening.

SAP 331-201-00080

## 12 Potential Clinical Relevance Criteria from Protocol

### Appendix 1 Criteria for Identifying Vital Signs of Potential Clinical Relevance

Variable	Criterion Value a	Change Relative to Baseline a
Heart Rate b	> 120 bpm < 50 bpm	≥ 15 bpm increase ≥ 15 bpm decrease
Systolic Blood Pressure b	> 180 mmHg < 90 mmHg	≥ 20 mmHg increase ≥ 20 mmHg decrease
Diastolic Blood Pressure b	> 105 mmHg < 50 mmHg	≥ 15 mmHg increase ≥ 15 mmHg decrease
Orthostatic Hypotension	≥ 20 mmHg decrease in systolic blood pressure and a ≥ 25 bpm increase in heart rate from supine to sitting/standing	Not Applicable (baseline status not considered)
Weight	-	≥ 7% increase ≥ 7% decrease

a In order to be identified as potentially clinically relevant, an on-treatment value must meet the “Criterion Value” and also represent a change from the subject’s baseline value of at least the magnitude shown in the “Change Relative to Baseline” column.

b As defined in “Supplementary Suggestions for Preparing an Integrated Summary of Safety Information in an Original NDA Submission and for Organizing Information in Periodic Safety Updates,” FDA Division of Neuropharmacological Drug Products draft (2/27/87).

SAP 331-201-00080

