Brexpiprazole (also referred to as OPC-34712 and Lu AF41156) is a novel atypical antipsychotic synthesized by Otsuka that is being codeveloped by Otsuka and Lundbeck. Brexpiprazole is currently approved in Canada and the US as monotherapy for the treatment of schizophrenia and the US for use as an adjunctive therapy to antidepressants for the treatment of major depressive disorder (MDD). While the precise mechanism of action of brexpiprazole in treating psychiatric conditions is unknown, the pharmacology of brexpiprazole is believed to be mediated by a combination of high binding affinity and functional activities at multiple monoaminergic receptors. It has modulatory activity at the serotonin (5-HT) and dopamine systems that combines partial agonist activity at serotonergic 5-HT_{1A} and at dopaminergic D₂ receptors with antagonist activity at serotonergic 5-HT_{2A} receptors, with similar high affinities at all of these receptors (K_i: 0.1 - 0.5 nM). Brexpiprazole also shows antagonist activity at noradrenergic α_{1B/2C} with affinity in the same subnanomolar K_i range (K_i: 0.2 - 0.6 nM). The 5-HT_{1A}/D₂ receptor partial agonist activity in combination with 5-HT_{2A} and α_{1B/2C} receptors antagonism of brexpiprazole may correlate with antipsychotic and antidepressant efficacy, reduced impulsive behavior, and cognitive improvement.⁷ This receptor activity profile may also prove an effective target for the treatment of acute mania of bipolar I disorder.

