18.	
Subjects with uncontrolled hypertension (DBP > 95 mmHg in any position) or symptomatic hypotension, or orthostatic hypotension which is defined as a decrease of ≥ 30 mmHg in SBP and/or a decrease of ≥ 20 mmHg in DBP after at least 3 minutes standing compared to the previous supine blood pressure, OR development of symptoms.
 
NOTE: Blood pressure measurements may be repeated once to ensure reproducibility of the exclusionary result(s) before excluding a subject based on the criteria noted above.

19.	Subjects with epilepsy or a history of seizures, except for a single seizure episode; for instance childhood febrile, post traumatic, or alcohol withdrawal seizure.
20.	Subjects with a history of a gastric bypass surgery that creates a malabsorptive state, including Roux-en-Y gastric bypass and biliopancreatic bypass with duodenal switch. This does not include gastric banding, gastric stapling, and sleeve gastrectomy procedures.

Protocol 331-201-00080

Table 3.4.3-1 Exclusion Criteria

Physical and Laboratory Results	
21.	Subjects with abnormal laboratory tests results, vital signs results, or ECG findings, unless, based on the investigator's judgment, the findings are not medically significant and would not impact the safety of the subject or the interpretation of the trial results. The medical monitor should be contacted to discuss individual cases, as needed. Criteria are provided in Section 3.7.3.2 . In addition, subjects with the following laboratory test and ECG results at screening must be excluded from the trial: 
 • Platelets \leq 75000/mm³ • Hemoglobin \leq 9 g/dL • Neutrophils, absolute \leq 1000/mm³ • AST $>$ 2 \times ULN • ALT $>$ 2 \times ULN • CPK $>$ 3 \times ULN, unless discussed with and approved by the medical monitor • Creatinine \geq 2 mg/dL • QTcF \geq 450 msec in men and \geq 470 msec in women, unless due to ventricular pacing. 
Tests with exclusionary results should be repeated to ensure reproducibility of the abnormality before excluding a subject based on the criteria noted above. For ECG, perform 3 consecutive recordings. If 2 of the 3 remain exclusionary then the subject must be excluded.

Disallowed and Concomitant Medication	
23.	Recent treatment with a long acting or depot antipsychotic in which the last dose was less than one full cycle plus 1/2 cycle from baseline visit (Section 4.1).

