Section 4.1, Prohibited Medications	However, subjects whose last injection of antipsychotic occurred at least one full cycle (based on the prescribing label) before the initial screening visit are eligible to enter the 14-day screening period if at least one full cycle plus 1/2 cycle (length of 1 cycle based on the prescribing label) will have elapsed before randomization. Other therapies restricted or prohibited prior to enrollment and during the trial are presented in Section 4.2.	However, subjects whose last injection of antipsychotic occurred at least one full cycle (based on the prescribing label) before the initial screening visit are eligible to enter the 14-day screening period if at least one full cycle plus 1/2 cycle (length of 1 cycle based on the prescribing label) will have elapsed before randomization. Subjects with serum concentrations of lithium ≥ 0.6 mmol/, valproate ≥ 50 μg/mL, or carbamazepine ≥ 4 μg/mL at screening may repeat a clinical laboratory test for these parameters prior to randomization. The results of the additional test will be reviewed and confirmed before the subject can be randomized into the trial. Other therapies restricted or prohibited prior to enrollment and during the trial are presented in Section 4.2.
Section 4.2, Other Restrictions	Not applicable (newly added text)	Anticholinergics are permitted for the treatment of EPS up to a maximum of 4 mg/day benztrapine or its equivalent and propranolol is permitted for akathisia or tremor up to a maximum of 20 mg 3 times daily (total of 60 mg/day). Sites should only utilize medications that are approved for these indications in their respective countries.

Protocol 331-201-00080

Section 5.1, Definitions	Pregnancies are also defined as IREs. Although normal pregnancy is not an AE, it will mandate IMP discontinuation and must be reported on an IRE form to the sponsor. Pregnancy will only be documented on the AE ePlatform if there is an abnormality or complication.	Pregnancies are also defined as IREs. Although normal pregnancy is not an AE, it will mandate IMP discontinuation and must be reported on the clinical trial pregnancy and breastfeeding form, or other designated form , to the sponsor. Pregnancy will only be documented on the AE ePlatform if there is an abnormality or complication.

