### 9.3 Vital Signs

Summary statistics for vital signs will be provided. For the double-blind treatment period, vital signs, change from baseline will be summarized for the Safety Sample by treatment group.

Potentially clinically relevant vital signs measurements identified in the double-blind treatment period for the Safety Sample will be summarized by treatment group. Criteria for identifying vital signs of potential clinical relevance are provided in [Appendix 1](#). All potentially clinically relevant events or changes will be listed and included in summary tables.

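### The on-treatment orthostatic hypotension flag requires a 25 bpm heart-rate rise that the trial's own exclusion definition does not, so it misses measured blood-pressure falls in both arms

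*SAP*

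**What the plan says.** The criterion for potentially clinically relevant orthostatic hypotension is "≥ 20 mmHg decrease in systolic blood pressure and a ≥ 25 bpm increase in heart rate from supine to sitting/standing" (SAP Appendix 1; identical in Protocol Appendix 2). Footnote a to that table makes the criterion value mandatory, so the heart-rate rise is a joint condition. The change-from-baseline column for this row reads "Not Applicable (baseline status not considered". SAP 9.3 gives the flag its use: "Potentially clinically relevant vital signs measurements identified in the double-blind treatment period for the Safety Sample will be summarized by treatment group".

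At entry, exclusion 18 (Protocol Table 3.4.3-1) bars subjects with "orthostatic hypotension which is defined as a decrease of ≥ 30 mmHg in SBP and/or a decrease of ≥ 20 mmHg in DBP". The fall is judged from supine to standing, and symptoms alone also qualify. Protocol 3.7.3.3.2 repeats this definition. Neither place mentions heart rate.

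The updated Section 4.2 text listed in Protocol Appendix 15 says that "propranolol is permitted for akathisia or tremor up to a maximum of 20 mg 3 times daily". Supine and standing blood pressure and heart rate are taken at every scheduled visit from screening to Day 21 (Protocol Table 3.7-1 and its vital-signs footnote).

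**The concern.** One named condition has two definitions that rest on different measurements. A subject whose systolic pressure falls 35 mmHg on standing with a 15 bpm heart-rate rise would have been barred at entry, yet on treatment the same reading does not enter the orthostatic row. A diastolic-only fall can never enter it. The visible text gives no reason for the heart-rate condition.

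Safety and tolerability is the secondary objective, and this flag is the only orthostatic criterion for measured values in the visible text. If it discards a large share of measured falls, the incidence by arm rests on few events and a difference between arms is harder to see. The heart-rate condition also sits awkwardly with a permitted beta-blocker, which raises the question of whether the loss could differ by arm.

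**Working it through.** The plan states no orthostatic rate, no propranolol-use rate and no precision target for this row, so there is no figure to reproduce.

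**Step 1. The two rules side by side.** Let s be the systolic fall, d the diastolic fall (mmHg) and h the heart-rate rise (bpm), supine to standing.
- SAP row: s ≥ 20 and h ≥ 25.
- Exclusion 18, blood-pressure part: s ≥ 30 or d ≥ 20.

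| s / d / h | SAP row | Exclusion 18, BP part |
|---|---|---|
| 35 / 10 / 10 | no | yes |
| 10 / 22 / 30 | no | yes |
| 35 / 22 / 24 | no | yes |
| 22 / 5 / 30 | yes | no |
| 20 / 5 / 25 | yes | no |
| 35 / 22 / 25 | yes | yes |

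Neither rule contains the other. The SAP's systolic cut is lower, but it adds the heart-rate condition and has no diastolic route.

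**Step 2. Do the other rows catch the missed cases?** Take 150/95 supine and 115/73 standing. The falls are 150 − 115 = 35 and 95 − 73 = 22 mmHg. The low-SBP row needs a value below 90 and the low-DBP row a value below 50, each with a decrease from baseline. Standing values of 115 and 73 meet neither. With a 15 bpm rise the orthostatic row is not met either, so this reading is unflagged.

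**Step 3. Illustrative size.** Expected count per arm = 160 × r × [(1 − u) × h0 + u × h1]. The 160 randomized per arm is from SAP 4. All else is assumed: r is the share with a systolic fall of at least 20 mmHg, u is propranolol use, and h0 and h1 are the shares of those falls with a rise of at least 25 bpm without and with propranolol.
- Without the heart-rate condition: 160 × 0.05 = 8 to 160 × 0.10 = 16 per arm.
- With it, u = 0 and h0 = 0.20 to 0.50: 8 × 0.20 = 1.6 to 16 × 0.50 = 8 per arm. The share lost is 1 − h0, or 50% to 80%, in both arms alike.

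**Step 4. Effect on the comparison when the loss is equal.** Assume r = 10% in one arm and 5% in the other.
- Blood pressure only: 16 against 8. Difference 8, ratio 2. SE of the log risk ratio = √(1/16 + 1/8 − 2/160) = √0.175 = 0.42.
- h0 = 0.50: 8 against 4. Difference 4, ratio 2, SE = √(1/8 + 1/4 − 2/160) = √0.3625 = 0.60.
- h0 = 0.20: 3.2 against 1.6. Difference 1.6, ratio 2, SE = √(1/3.2 + 1/1.6 − 2/160) = √0.925 = 0.96.

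The expected ratio is unchanged. The absolute difference shrinks by the factor h0, and the standard error of the log ratio grows from 0.42 to between 0.60 and 0.96.

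**Step 5. Could propranolol make the loss unequal?** Take equal r in both arms, so the true ratio is 1.00. The counted ratio (higher-use arm over lower-use arm) is [(1 − u1)h0 + u1h1] / [(1 − u2)h0 + u2h1].
- Use 10% against 2%: h1 = 0 gives 0.90/0.98 = 0.918; h1 = h0/2 gives 0.95/0.99 = 0.960; h1 = h0 gives 1.000.
- Use 20% against 5%: h1 = 0 gives 0.80/0.95 = 0.842; h1 = h0/2 gives 0.90/0.975 = 0.923; h1 = h0 gives 1.000.

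The range is 0.84 to 1.00. It is 1.00 if use is balanced or the rise is not limited.

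**The case against.** **Entry and on-treatment criteria differ elsewhere by design.** AST and ALT exclude above 2 × ULN but flag at 3 × ULN or more. Diastolic pressure excludes above 95 mmHg but flags above 105 with a change from baseline. Hemoglobin excludes at 9 g/dL or below but flags at 11.5 (men) or 9.5 (women) or below. This stands: a mismatch with exclusion 18 is not in itself an error, and the SAP applies the protocol's own criterion faithfully. But those examples move a cut-off on the same measurement. The orthostatic row adds a second vital sign and drops the diastolic one.

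**Other reporting exists.** Orthostatic hypotension reported as an adverse event is tabulated by arm under SAP 9.1 with no heart-rate rule, and SAP 9.3 summarizes vital-sign changes. Part of the adverse-event section and the list of tables are blacked out, so further orthostatic output cannot be ruled out. This limits the claim to the measured-value flag. Adverse-event tables depend on what is reported and do not replace a prospectively defined criterion on measured values.

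**Stronger readings that the documents do not support.** A reader might infer:
- that cases are lost mainly in the brexpiprazole arm through propranolol. The documents give no akathisia, tremor or propranolol rates by arm and do not say that propranolol limits the rise. The body of Section 4.2 is not in the text available here, so further conditions on its use could not be checked.
- that the comparison is biased toward no difference on every scale. Step 4 shows that equal loss leaves the expected risk ratio unchanged.
- that exclusion 18 uses blood pressure alone. Symptoms also qualify.
- that the receptor profile and faster titration make an excess foreseeable. The protocol draws no such link, and its Section 2.2 reports similar safety and tolerability with higher starting doses and faster titration.

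**Conclusion.** The point holds as a limited reporting weakness. By its wording, the SAP row cannot count a systolic fall of any size without a 25 bpm rise, or any diastolic-only fall, including falls that would have barred entry. That part follows from the documents without assumptions. It means an under-count of measured falls in both arms, with a smaller absolute difference and less precision.

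The size is not known. The 50% to 80% loss and the standard errors above rest on assumed rates and on the same h0 in both arms. A loss as high as 70% to 99% could be produced by assuming a distribution for the standing heart-rate rise, but such inputs have no source in the documents, and the top of that range would apply only to propranolol users. A difference in under-counting between arms is possible if propranolol use differs and it limits the rise; its size and direction are unknown. This is a cheap improvement to safety reporting and does not touch the efficacy conclusions.

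**What to change.** This changes reporting only, not clinical management.
- Reconcile the two definitions in the SAP, with a sentence on why the on-treatment flag differs from exclusion 18. State the position as supine to standing, since the criterion also names sitting, which the protocol does not measure.
- Keep the present row in the SAP 9.3 incidence table and add two rows by treatment arm: (a) the blood-pressure part of exclusion 18 (SBP fall ≥ 30 and/or DBP fall ≥ 20 mmHg); (b) the SAP's own SBP fall ≥ 20 mmHg without the heart-rate condition.
- Show propranolol use for flagged subjects in a listing. Do not compare arms within propranolol strata: use is post-randomization and may be affected by treatment, so that comparison is not randomized.

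Cost: SAP wording and one or two table rows. Supine and standing readings and concomitant medications are already collected. The downside is a higher reported incidence in both arms.

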**Appendix 2****Criteria for Identifying Laboratory Values of Potential Clinical Relevance**

Laboratory Tests	Criteria
Chemistry	
AST (SGOT)	$\geq 3 \times$ upper limit of normal (ULN)
ALT (SGPT)	$\geq 3 \times$ ULN
Alkaline phosphatase	$\geq 3 \times$ ULN
Lactate dehydrogenase (LDH)	$\geq 3 \times$ ULN
Blood urea nitrogen (BUN)	$\geq 30$ mg/dL
Creatinine	$\geq 2.0$ mg/dL
Uric Acid	
Men	$\geq 10.5$ mg/dL
Women	$\geq 8.5$ mg/dL
Bilirubin (total)	$\geq 2.0$ mg/dL
Creatine phosphokinase (CPK)	$\geq 3 \times$ ULN
Prolactin	$>$ ULN
Hematology	
Hematocrit	
Men	$\leq 37\%$ and decrease of $\geq 3$ percentage points from Baseline
Women	$\leq 32\%$ and decrease of $\geq 3$ percentage points from Baseline
Hemoglobin	
Men	$\leq 11.5$ g/dL
Women	$\leq 9.5$ g/dL
White blood count	$\leq 2,800/\text{mm}^3$ or $\geq 16,000/\text{mm}^3$
Eosinophils	$\geq 10\%$
Neutrophils	$\leq 15\%$
Absolute neutrophil count	$\leq 1,000/\text{mm}^3$
Platelet count	$\leq 75,000/\text{mm}^3$ or $\geq 700,000/\text{mm}^3$
Urinalysis	
Protein	Increase of $\geq 2$ units
Glucose	Increase of $\geq 2$ units
Casts	Increase of $\geq 2$ units
Additional Criteria	
Chloride	$\leq 90$ mEq/L or $\geq 118$ mEq/L
Potassium	$\leq 2.5$ mEq/L or $\geq 6.5$ mEq/L
Sodium	$\leq 126$ mEq/L or $\geq 156$ mEq/L
Calcium	$\leq 8.2$ mg/dL or $\geq 12$ mg/dL
Glucose	
Fasting	$\geq 100$ mg/dL
Non-Fasting	$\geq 200$ mg/dL
Total Cholesterol, Fasting	$\geq 240$ mg/dL
LDL Cholesterol, Fasting	$\geq 160$ mg/dL
HDL Cholesterol, Fasting	
Men	$< 40$ mg/dL
Women	$< 50$ mg/dL
Triglycerides, Fasting	$\geq 150$ mg/dL

SAP 331-201-00080

20	480
21	480
22	480
23	480
24	480
25	480
26	480
27	480
28	480
29	480
30	480
31	480
32	480
33	480
34	480
35	480
36	480
37	480
38	480
39	480
40	480
41	480
42	480
43	480
44	480
45	480
46	480
47	480
48	480
49	480
50	480
51	480
52	480
53	480
54	480
55	480
56	480
57	480
58	480
59	480
60	480
61	480
62	480
63	480
64	480
65	480
66	480
67	480
68	480
69	480
70	480
71	480
72	480
73	480
74	480
75	480
76	480
77	480
78	480
79	480
80	480
81	480
82	480
83	480
84	480
85	480
86	480
87	480
88	480
89	480
90	480
91	480
92	480
93	480
94	480
95	480
96	480
97	480
98	480
99	480
100	480
101	480
102	480
103	480
104	480
105	480
106	480
107	480
108	480
109	480
110	480
111	480
112	480
113	480
114	480
115	480
116	480
117	480
118	480
119	480
120	480
121	480
122	480
123	480
124	480
125	480
126	480
127	480
128	480
129	480
130	480
131	480
132	480
133	480
134	480
135	480
136	480
137	480
138	480
139	480
140	480
141	480
142	480
143	480
144	480
145	480
146	480
147	480
148	480
149	480
150	480
151	480
152	480
153	480
154	480
155	480
156	480
157	480
158	480
159	480
160	480
161	480
162	480
163	480
164	480
165	480
166	480
167	480
168	480
169	480
170	480
171	480
172	480
173	480
174	480
175	480
176	480
177	480
178	480
179	480
180	480
181	480
182	480
183	480
184	480
185	480
186	480
187	480
188	480
189	480
190	480
191	480
192	480
193	480
194	480
195	480
196	480
197	480
198	480
199	480
200	480
201	480
202	480
203	480
204	480
205	480
206	480
207	480
208	480
209	480
210	480
211	480
212	480
213	480
214	480
215	480
216	480
217	480
218	480
219	480
220	480
221	480
222	480
223	480
224	480
225	480
226	480
227	480
228	480
229	480
230	480
231	480
232	480
233	480
234	480
235	480
236	480
237	480
238	480
239	480
240	480
241	480
242	480
243	480
244	480
245	480
246	480
247	480
248	480
249	480
250	480
251	480
252	480
253	480
254	480
255	480
256	480
257	480
258	480
259	480
260	480
261	480
262	480
263	480
264	480
265	480
266	480
267	480
268	480
269	480
270	480
271	480
272	480
273	480
274	480
275	480
276	480
277	480
278	480
279	480
280	480
281	480
282	480
283	480
284	480
285	480
286	480
287	480
288	480
289	480
290	480
291	480
292	480
293	480
294	480
295	480
296	480
297	480
298	480
299	480
300	480
301	480
302	480
303	480
304	480
305	480
306	480
307	480
308	480
309	480
310	480
311	480
312	480
313	480
314	480
315	480
316	480
317	480
318	480
319	480
320	480
321	480
322	480
323	480
324	480
325	480
326	480
327	480
328	480
329	480
330	480
331	480
332	480
333	480
334	480
335	480
336	480
337	480
338	480
339	480
340	480
341	480
342	480
343	480
344	480
345	480
346	480
347	480
348	480
349	480
350	480
351	480
352	480
353	480
354	480
355	480
356	480
357	480
358	480
359	480
360	480
361	480
362	480
363	480
364	480
365	480
366	480
367	480
368	480
369	480
370	480
371	480
372	480
373	480
374	480
375	480
376	480
377	480
378	480
379	480
380	480
381	480
382	480
383	480
384	480
385	480
386	480
387	480
388	480
389	480
390	480
391	480
392	480
393	480
394	480
395	480
396	480
397	480
398	480
399	480
400	480
401	480
402	480
403	480
404	480
405	480
406	480
407	480
408	480
409	480
410	480
411	480
412	480
413	480
414	480
415	480
416	480
417	480
418	480
419	480
420	480
421	480
422	480
423	480
424	480
425	480
426	480
427	480
428	480
429	480
430	480
431	480
432	480
433	480
434	480
435	480
436	480
437	480
438	480
439	480
440	480
441	480
442	480
443	480
444	480
445	480
446	480
447	480
448	480
449	480
450	480
451	480
452	480
453	480
454	480
455	480
456	480
457	480
458	480
459	480
460	480
461	480
462	480
463	480
464	480
465	480
466	480
467	480
468	480
469	480
470	480
471	480
472	480
473	480
474	480
475	480
476	480
477	480
478	480
479	480
480	480
481	480
482	480
483	480
484	480
485	480
486	480
487	480
488	480
489	480
490	480
491	480
492	480
493	480
494	480
495	480
496	480
497	480
498	480
499	480
500	480

SAP 331-201-00080

SAP 331-201-00080

SAP 331-201-00080

SAP 331-201-00080

Horizontal bar chart showing CCI and CCI' values for 100 samples. The y-axis is labeled "Sample" and ranges from 1 to 100. The x-axis is labeled "Value" and ranges from 0 to 1.0. CCI values are in red, and CCI' values are in blue.

Sample	CCI	CCI'
1	0.55	0.55
2	0.55	0.55
3	0.55	0.55
4	0.55	0.55
5	0.55	0.55
6	0.55	0.55
7	0.55	0.55
8	0.55	0.55
9	0.55	0.55
10	0.55	0.55
11	0.55	0.55
12	0.55	0.55
13	0.55	0.55
14	0.55	0.55
15	0.55	0.55
16	0.55	0.55
17	0.55	0.55
18	0.55	0.55
19	0.55	0.55
20	0.55	0.55
21	0.55	0.55
22	0.55	0.55
23	0.55	0.55
24	0.55	0.55
25	0.55	0.55
26	0.55	0.55
27	0.55	0.55
28	0.55	0.55
29	0.55	0.55
30	0.55	0.55
31	0.55	0.55
32	0.55	0.55
33	0.55	0.55
34	0.55	0.55
35	0.55	0.55
36	0.55	0.55
37	0.55	0.55
38	0.55	0.55
39	0.55	0.55
40	0.55	0.55
41	0.55	0.55
42	0.55	0.55
43	0.55	0.55
44	0.55	0.55
45	0.55	0.55
46	0.55	0.55
47	0.55	0.55
48	0.55	0.55
49	0.55	0.55
50	0.55	0.55
51	0.55	0.55
52	0.55	0.55
53	0.55	0.55
54	0.55	0.55
55	0.55	0.55
56	0.55	0.55
57	0.55	0.55
58	0.55	0.55
59	0.55	0.55
60	0.55	0.55
61	0.55	0.55
62	0.55	0.55
63	0.55	0.55
64	0.55	0.55
65	0.55	0.55
66	0.55	0.55
67	0.55	0.55
68	0.55	0.55
69	0.55	0.55
70	0.55	0.55
71	0.55	0.55
72	0.55	0.55
73	0.55	0.55
74	0.55	0.55
75	0.55	0.55
76	0.55	0.55
77	0.55	0.55
78	0.55	0.55
79	0.55	0.55
80	0.55	0.55
81	0.55	0.55
82	0.55	0.55
83	0.55	0.55
84	0.55	0.55
85	0.55	0.55
86	0.55	0.55
87	0.55	0.55
88	0.55	0.55
89	0.55	0.55
90	0.55	0.55
91	0.55	0.55
92	0.55	0.55
93	0.55	0.55
94	0.55	0.55
95	0.55	0.55
96	0.55	0.55
97	0.55	0.55
98	0.55	0.55
99	0.55	0.55
100	0.55	0.55

SAP 331-201-00080

Horizontal bar chart showing the percentage of countries with different CCI scores. The x-axis represents the percentage from 0% to 100%. The y-axis lists CCI scores from 0 to 10. The bars are black with white outlines. The legend indicates that the first bar (0-1) is red, and the others are black.

CCI Score	Percentage
0-1	~10%
2-3	~15%
4-5	~10%
6-7	~10%
8-9	~10%
10	~10%
11-12	~10%
13-14	~10%
15-16	~10%
17-18	~10%
19-20	~10%
21-22	~10%
23-24	~10%
25-26	~10%
27-28	~10%
29-30	~10%
31-32	~10%
33-34	~10%
35-36	~10%
37-38	~10%
39-40	~10%
41-42	~10%
43-44	~10%
45-46	~10%
47-48	~10%
49-50	~10%
51-52	~10%
53-54	~10%
55-56	~10%
57-58	~10%
59-60	~10%
61-62	~10%
63-64	~10%
65-66	~10%
67-68	~10%
69-70	~10%
71-72	~10%
73-74	~10%
75-76	~10%
77-78	~10%
79-80	~10%
81-82	~10%
83-84	~10%
85-86	~10%
87-88	~10%
89-90	~10%
91-92	~10%
93-94	~10%
95-96	~10%
97-98	~10%
99-100	~10%

